## 6.7.5 Urinalysis

Urinalysis data will be presented as detailed in the protocol under ‘Clinical laboratory evaluation’, Section 14.3.9.3.

Potentially clinically significant values will be defined as displayed in [Table 4](#).

**Table 4: Potentially clinically significant urinalysis values**

Protocol lab parameter (Central lab parameter)	SI Unit	PCS low	PCS High
Erythrocytes	/HPF	N/A	> 3, >10, >25, >50
Leucocytes	/HPF	N/A	> 10
Casts (Hyaline casts)	/LPF	N/A	> 2
Casts (WBC casts)	/LPF	N/A	Few, Moderate, Many
Casts (RBC casts)	/LPF	N/A	Few, Moderate, Many
Casts (Waxy casts)	/LPF	N/A	Few, Moderate, Many
Casts (Granular casts)	/LPF	N/A	Few, Moderate, Many

PCS: potentially clinically significant; HPF: high power field; LPF: low power field;

### 6.7.6 Pharmacokinetics and anti-drug antibodies

Pharmacokinetics and anti-drug antibodies data will be summarised as detailed in the protocol, but for the treatment period only.

An extra summarisation will be made over ADA status across the entire trial.

## 6.8 General Principles

### 6.8.1 Baseline value

Unless otherwise specified, the baseline value is defined as the latest pre-dose assessment.

#### Missing baseline assessments

When the baseline value is missing, endpoints concerning a change from baseline cannot be derived, and such subjects will be excluded from the analysis. Since the missingness of baseline values is unrelated to the assigned treatment, bias should not be a concern with this approach.

### 6.8.2 Definition of trial periods, date of permanent discontinuation of IMP and start of the COVID-19 pandemic

#### Date of permanent discontinuation of IMP

Defined for subjects who have a reason for permanent discontinuation of IMP recorded.

The latest date of either is the date of permanent discontinuation of IMP: The date of early termination visit (if existing) or the date of onset of latest AE leading to withdrawal of IMP (if existing). Otherwise, the date of the last visit, excluding safety follow-up, nominal Week 16 visit and nominal Week 26 visit, unless the last visit is the Week 26 visit in which case the subsequent scheduled visit following the last administered IMP dose will be used (observed date (if existing) else planned date + 7 days).

Unscheduled visits can be used as the date of permanent discontinuation of IMP if the unscheduled visit is within the window for where subjects can be dosed. This means that only unscheduled visits between the baseline visit and the Week 24 visit (if existing), or the planned visit + 7 days will be used to account for the visit window.

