14.3.7 Intercurrent events

The applied estimands incorporate the following 3 main subject-specific intercurrent events that influence how the treatment effects are estimated.

- **Initiation of rescue treatment:**

Some of the estimands use the initiation of rescue treatment as an event that modifies the applied value of an endpoint, e.g. by defining a subject receiving rescue treatment as a non-responder.

- **Permanent discontinuation of IMP:**

This event occurs when a subject is permanently withdrawn from the treatment or the trial

as described in Section 10.3. This can be at the subject's own initiative, at the investigator's discretion, or if the subject is lost to follow-up. The timing of the event is defined as the date of the early termination visit for withdrawn subjects or – in the case of a subject lost to follow-up – the date of the last known visit to the clinic. As for the rescue treatment, the event is used to modify an applied endpoint value.

- **Subject-onset of the COVID-19 pandemic:**

This event is introduced to mitigate the external influence that the occurrence of the COVID-19 pandemic could have on the compliance of a subject with planned trial procedures and on the resulting interpretation of the trial.

The event reflects the first occasion when the COVID-19 pandemic prevents a subject from complying with the protocol in a substantial manner. As described in Section 14.3.1, the circumstances arising from the COVID-19 pandemic might for example prevent a subject from receiving IMP or from conducting visits to the site, whereby planned assessments and procedures could become missing.

For a given subject, this event is defined as the first occurrence of either of the 3 underlying COVID-19 pandemic-related scenarios defined in Section 14.3.1:

- Permanent discontinuation of IMP due to the COVID-19 pandemic.
- Use of rescue treatment due to unavailability of IMP related to the COVID-19 pandemic.
- Prolonged interruption of IMP dosing due to the COVID-19 pandemic.

As for the other 2 intercurrent events (initiation of rescue treatment and permanent discontinuation of IMP), collected and/or missing data following the start of the event will be handled differently from other data in especially the 'COVID-19 modified composite' estimand.

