#### Assignment of AEs to periods

An AE will be assigned to a given period (treatment or safety follow-up) if the start date of the AE is after the start date and before or at the end date of that period (see Section 6.8.2, Table 6).

For AEs with start day on the same day as the first dose was given, only AEs starting after the first dose was given will be considered treatment emergent and assigned to the treatment period.

For the handling of incomplete start dates of AEs, see Section 6.8.3.

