#### Exposure end

Date of Week 26 visit (if existing) at time 23:59:50, otherwise date of permanent discontinuation of IMP (if existing) at time 23:59:50, otherwise date of last IMP administration at time 23:59:00.

Trial ID: LP0162-1346	Date: 21-OCT-2020	Version: v1.0 Page 25 of 35
-----------------------	-------------------	--------------------------------

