### 6.8.6 Timing of intercurrent events

Actions taken based on intercurrent events will be dependent on whether or not an intercurrent event happens prior to a relevant visit. The rule will be that if any regarded intercurrent event happens prior to the date of the visit then the intercurrent event will be defined to be prior to the relevant visit. The following list of dates will be used in a prioritised manner as the date of the visit, i.e. if a date higher in the hierarchy exists that date will be used:

1. Observed date of the visit. When no data is available from the scheduled visit, data and visit date can be mapped to the visit per the rules stated in Section 6.8.4.
2. Planned date of the visit – 7 days, to account for the visit window.

In case intercurrent events occurs on the same date the following prioritise list will be used: rescue treatment, permanent discontinuation of IMP, and then subject-onset of the COVID-19 pandemic.

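### Without an early termination visit, the SAP dates IMP discontinuation at AE onset, which can fall before doses that were still given; a last-dose floor is needed

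*SAP*

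**What the plan says.** For subjects with a recorded reason for stopping IMP, SAP 6.8.2 states: "The latest date of either is the date of permanent discontinuation of IMP". The two candidates are the early termination (ET) visit "or the date of onset of latest AE leading to withdrawal of IMP (if existing). Otherwise, the date of the last visit". The last visit is therefore a fallback, reached only when there is neither an ET visit nor an AE leading to withdrawal. The last administered dose enters the rule only in the exception for a last visit at Week 26.

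Other rules use this date:

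- **Timing (SAP 6.8.6):** "if any regarded intercurrent event happens prior to the date of the visit then the intercurrent event will be defined to be prior" to that visit.
- **Primary estimand (protocol 14.3.8.1, Panel 13; SAP Table 9):** once discontinuation is the first prior event, even observed data are set to non-response. The composite estimand does the same.
- **Models (protocol 14.3.8.1, 14.3.8.4, 14.3.9.1):** data after discontinuation are left out of the imputation and hypothetical models.
- **Exposure end (SAP 6.8.2):** a Week 26 visit, where there is one, sets the date. For everyone else the order is "otherwise date of permanent discontinuation of IMP (if existing) at time 23:59:50, otherwise date of last IMP administration at time 23:59:00".
- **AE periods (SAP 6.7.1):** an AE belongs to a period "if the start date of the AE is after the start date and before or at the end date of that period". The section says the split is meant to separate AEs on active treatment from those off it.

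Protocol 14.3.7 dates the event at the ET visit for withdrawn subjects and, for those lost to follow-up, at "the date of the last known visit to the clinic". AE onset is not among its dates.

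**The concern.** An AE can begin well before IMP is stopped because of it. Protocol 10.2.1 contains a case of this kind: one transaminase criterion requires the elevation to last more than two weeks. With no ET visit, the SAP rule can then place discontinuation before doses that were actually given.

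Two things are at stake. In efficacy, a response seen under continued dosing is scored as a failure, although the protocol's reason for non-response is that a response after stopping cannot be credited to the randomised treatment. In safety, events that start while the subject is still being injected can be reported as off-treatment.

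**Working it through.** **Planned power, for scale.** Inputs from protocol 7.1 and 14.1: n = 125 per arm, 40% vs 15%, two-sided 5%. With pooled null variance,

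z = [|p1 − p2|·√n − 1.96·√(2·p̄·(1 − p̄))] / √(p1(1 − p1) + p2(1 − p2))

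= [0.25 × 11.180 − 1.96 × √(2 × 0.275 × 0.725)] / √(0.24 + 0.1275) = (2.795 − 1.238) / 0.606 = 2.57,

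so power is 99.5%, which agrees with the stated 99%.

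**Applying the date rules.** The subject is assumed, not taken from the documents: AE onset Day 70, dosing continued to the Week 16 visit on Day 112, last visit Day 126, IMP stopped for the AE, no earlier rescue treatment or COVID-19 subject-onset.

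| Case | Discontinuation date | Week 16 (Day 112) | Exposure end | Exposure end minus last dose |
|---|---|---|---|---|
| (a) no ET, no Week 26 visit | Day 70 | 70 < 112: non-response | Day 70 | −42 days |
| (b) as (a), ET on Day 126 | max(126, 70) = Day 126 | observed value used | Day 126 | +14 days |
| (c) as (a), no AE recorded as leading to withdrawal | last visit, Day 126 | observed value used | Day 126 | +14 days |
| (d) as (a), Week 26 visit on Day 182 | Day 70 | non-response | Day 182 | +70 days |
| (a) with last-dose floor | max(70, 112) = Day 112 | not prior: observed value used | Day 112 | 0 days |

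In (a), the doses at Weeks 12, 14 and 16 (Days 84, 98, 112) all fall after the nominal end of exposure. Under treatment policy the observed Week 16 value is kept, but the subject joins the discontinued group, so on-treatment data inform imputation for subjects who really had stopped.

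At Week 26 the path is narrower. The last planned dose is at Week 24, so the subject would have to be dosed through Week 24 and still be recorded as discontinued.

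**Effect of reclassification.** One tralokinumab responder lost is 1/125 = 0.8 points. With 1, 3 or 5 lost (assumed, all in that arm), the rate is 39.2%, 37.6% or 36.0%, and power is 99.3%, 98.5% or 97.2%.

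**How many subjects.** All rates here are assumptions except the response rates. AE withdrawals of 2–5% give about 5–12 of 250. If a quarter to a half lack an ET visit, about 1–6 take an AE-onset date. If 20–40% of those straddle Week 16 and 15–40% respond, the expected number reclassified runs from 1 × 0.20 × 0.15 = 0.03 to 6 × 0.40 × 0.40 = 0.96 in the whole trial.

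**The case against.** The strongest reply is that the conditions rarely coincide. Protocol Panel 6 asks for an ET visit at every stage of discontinuation. Several listed stopping reasons, such as anaphylaxis, would normally put onset close to stopping. The SAP uses the latest relevant AE, and Appendix 2 has a worsening AE recorded anew with a later onset. This stands as an argument about size. It does not remove the defect: ET visits are requested rather than guaranteed, the SAP itself provides for their absence, and an AE of constant severity keeps its first onset date.

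A reader might infer three stronger claims, none of which the documents support:

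- **That the SAP overrides a protocol date.** Protocol 14.3.7 gives no date for a subject withdrawn for an AE, without an ET visit and not lost to follow-up. There the SAP fills a gap, although SAP 6.6.1 presents intercurrent events as following the protocol and the change log does not mention the rule.
- **That the result is biased in a known direction.** The rule is the same in both arms, and protocol 5.6 describes an AE profile comparable to placebo.
- **That exposure is always cut short.** A Week 26 visit takes precedence, as in case (d). Whether a nominal Week 26 visit counts is not stated.

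**Conclusion.** The point holds as a derivation error with narrow reach. On the SAP's own wording, an AE withdrawal without an ET visit can be dated before later doses. An on-treatment Week 16 assessment then becomes non-response in the COVID-19 modified composite and composite estimands and drops out of the imputation and hypothetical models. Without a Week 26 visit, exposure also ends before the last dose, and AEs arising under dosing are tabulated as follow-up events, against the stated purpose of the split.

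The size is small: on the assumed rates, no more than about one expected reclassification in 250 subjects, and power still above 97% with five. The number affected is not in the documents, and the power figures assume that every reclassified subject is a tralokinumab responder. The reason to act is that the rule can yield an impossible date and is almost free to correct.

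**What to change.** In SAP 6.8.2, state that without an ET visit the discontinuation date is the later of the AE onset date and the date of the last IMP administration, and that exposure end may not precede the last IMP administration. Reconcile this with the event timing in protocol 14.3.7, and say whether a nominal Week 26 visit counts for exposure end.

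Do not carry over the next-scheduled-visit wording from the SAP's Week 26 exception. Take a last dose on Day 98, AE onset on Day 100, no ET visit, and a nominal Week 16 visit on Day 112. The present rule and the proposed floor both give Day 100, hence non-response. The next-visit wording gives Day 112 (observed) or Day 119 (planned + 7). Neither is prior to the visit, so an off-treatment response would count as success.

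The floor leaves one case open: a subject given the Week 24 dose and still recorded as discontinued would be dated at Week 24, before the Week 26 visit. The text should say whether such a subject counts as having discontinued.

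The cost is a few sentences of SAP text and a line or two of derivation code. Protocol 9.8.3 already has dosing dates recorded in the eCRF.

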#### Exposure start

Date and time of first dose.

#### Exposure end

Date of Week 26 visit (if existing) at time 23:59:50, otherwise date of permanent discontinuation of IMP (if existing) at time 23:59:50, otherwise date of last IMP administration at time 23:59:00.

Trial ID: LP0162-1346	Date: 21-OCT-2020	Version: v1.0 Page 25 of 35
-----------------------	-------------------	--------------------------------

### Date of last contact

Date of very last contact found by examining all time and date information in eCRF, laboratory, ECG, PRO and eDiary data.

### Start of the COVID-19 pandemic

The start of the COVID-19 pandemic will be set to the 1st of March 2020 at time 00:00:00 across the whole trial. The date was decided based on the fact that at this date the trial procedures were most likely not impacted by the COVID-19 pandemic but still keeping it as close as possible to the first observed occurrence of missed procedures due to the COVID-19 pandemic.

### Trial periods

For efficacy assessments the analysis set are defined only for the treatment period which is listed in [Table 5](#) (ADaM variable APERIOD).

For safety assessments, the two analysis sets are defined by a start and end of each period which are listed in [Table 6](#) (ADaM variable APHASE).

Additionally, a sub-trial period is defined for the safety assessments considering the COVID-19 pandemic. For this we define the start and stop for the treatment and safety follow-up periods prior to and after the start of the COVID-19 pandemic which are listed in [Table 7](#).

**Table 5: Start and end time of trial periods (ADaM variable APERIOD)**

APERIOD	Start of period	End of period (only if start date exists)
Treatment period	Exposure start	Date of last contact at time 23:59:59

**Table 6: Start and end time of trial periods (ADaM variable APHASE)**

APHASE	Start of period	End of period (only if start date exists)
Treatment period	Exposure start	Exposure end
Safety follow-up period	Exposure end (plus 1 second)	Date of safety follow-up visit (if existing) at time 23:59:59 else

		Date of last contact at time 23:59:59
--	--	---------------------------------------

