- Tralokinumab 300 mg Q2W: tralokinumab 600 mg (loading dose) at baseline, then tralokinumab 300 mg Q2W.
- Placebo Q2W: placebo (loading dose) at baseline, then placebo Q2W.

The last dose of IMP will be administered at Week 24.

Subjects in both treatment groups will apply a thin film of a supplied TCS once daily to areas with active lesions as needed; lower potency TCS or TCI may be prescribed if needed on body areas where the supplied TCS is not advisable or on areas where continued treatment with TCS is considered unsafe. Topical therapy will be discontinued when control is achieved; discontinuation should preferably be gradual. The safety and appropriateness of continued or repeated courses of TCS therapy will be monitored and supervised by the site staff.

Safety follow-up period (Week 26 to Week 40)

Subjects, except those who enter the long-term extension trial (LP0162-1337, ECZTEND, see below), will complete a 14-week off-treatment follow-up period for the assessment of safety, PK, and ADA.

Long-term extension trial (selected countries)

Eligible subjects may be invited to enter a long-term extension trial conducted under a separate protocol (LP0162-1337, ECZTEND). Subjects who transfer to ECZTEND must have had their last visit in the treatment period (Week 26 under the current protocol).

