14.2 Trial analysis sets

All screened subjects will be accounted for in the CTR.

All subjects randomised to treatment and exposed to the IMP will be included in the full analysis set (FAS) and will be analysed for efficacy. Exclusions from the FAS can be considered in special cases as described in the ICH E9 guideline, Section 5.2.1 (37). If it is decided to exclude a randomised subject from the FAS, a justification addressing ICH E9 will be given.

The following safety analysis sets are applied:

- ‘safety analysis set’ for all subjects exposed to IMP within the treatment period.
- ‘safety follow-up analysis set’ for all subjects exposed to IMP within the safety follow-up period.

The decisions regarding inclusion/exclusion of subjects from the trial analysis sets will be documented in the analysis set definition document before breaking the randomisation code.

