### 6.2 Disposition

Subject disposition will be summarised as detailed in the protocol.

Additionally, reasons for not attending the nominal Week 16 and Week 26 visits will be summarised for randomised subjects. Not attending the nominal Week 16 and Week 26 visits due to the COVID-19 pandemic will be added to the list of reasons based on the information documented in the eCRF. Technical aspects of attributing missed visits to the COVID-19 pandemic is further detailed in Section 6.8.8.

The number of randomised subjects and screen failures will be summarised for all screened subjects. Screen failures will be summarised by reason as well as overall.

For the safety follow-up visit, attendance will be summarised for all subjects included in the safety follow-up analysis set. Not attending the safety follow-up visit due to the COVID-19

Trial ID: LP0162-1346	Date: 21-OCT-2020	Version: v1.0 Page 10 of 35
-----------------------	-------------------	--------------------------------

pandemic will be added to the list of reasons, as for reasons for not attending the nominal Week 16 and Week 26 visits.

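### The SAP's period rule puts subjects who transfer to ECZTEND at Week 26 into the safety follow-up analysis set, which lowers the follow-up AE percentages

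*SAP*

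**What the plan says.** Protocol 14.2 describes the safety follow-up analysis set as being "for all subjects exposed to IMP within the safety follow-up period". Section 7.1 states that "The last dose of IMP will be administered at Week 24". It also says that subjects, other than those entering ECZTEND, "will complete a 14-week off-treatment follow-up period for the assessment of safety, PK, and ADA". Panel 3, footnote 2, makes the last visit before transfer the end-of-trial visit for ECZTEND entrants, so they have no follow-up visit here. Under Protocol 13.2, an entrant's AE is reported in this trial if it starts before the final visit.

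SAP 5 refers to the protocol for the analysis sets and elaborates only the FAS. The working rule is in SAP 6.8.2: "For safety assessments, the two analysis sets are defined by a start and end of each period which are listed in" Table 6. Exposure end is "Date of Week 26 visit (if existing) at time 23:59:50". Table 6 opens follow-up at "Exposure end (plus 1 second" and closes it on the follow-up visit date or, failing that, the last-contact date, in both cases at 23:59:59.

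The set is used in two kinds of output. SAP 6.7.1 splits AE summaries into treatment and follow-up periods, with the measures taken from Protocol 14.3.13.1: number and percentage of subjects, and event rate. SAP 6.2 adds: "For the safety follow-up visit, attendance will be summarised for all subjects included in the safety follow-up analysis set".

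**The concern.** Follow-up AE tables should describe subjects who were observed off treatment. If the set also holds subjects whose participation ended at Week 26, those subjects count in the denominator and can practically never count in the numerator. The percentages then understate how often off-treatment AEs occur, and the size of the understatement depends on how many subjects transferred. Any chi-square or Fisher's exact test on these percentages, as Protocol 14.3.13.1 plans for AEs, would use the same denominators.

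The attendance table has the same fault. Transferring subjects would appear as not having attended a visit they were never due to make, although Protocol 7.3 counts them as trial completers. The reasons listed in Protocol 11.8 for missing that visit include no category for entering ECZTEND.

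**Working it through.** The documents give neither a size for this set nor a transfer share, so there is no stated figure to reproduce. The check is clock arithmetic followed by a dilution formula.

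**1. Length of follow-up for a subject transferring at Week 26** (SAP 6.8.2 and Table 6)
- Exposure end: Week 26 date, 23:59:50.
- Follow-up start: 23:59:50 + 1 s = 23:59:51.
- Follow-up end, with no follow-up visit and last contact on the Week 26 date: 23:59:59.
- Length: 23:59:59 − 23:59:51 = 8 s.

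The date of last contact is the latest date in any data source, so it cannot precede the Week 26 visit. A later stray date lengthens the interval and the subject still qualifies, so 8 s is the minimum. Membership rests on the clock convention: had exposure end been set at 23:59:59, the interval would be −1 s and the subject would drop out.

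**2. Can such a subject contribute a follow-up AE?** SAP 6.7.1 needs an onset after the period start, which is the last seconds of the Week 26 date. Protocol 13.2 limits an entrant's reported AEs to those starting before the final visit. In practice the answer is no.

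**3. Comparison with the stated expectation.** Protocol 14.3.13.2 and 14.3.13.3 only list vital signs and laboratory values for this set. The Amendment 3 summary gives the reason for that current text: so many subjects go on to ECZTEND that too few are expected to justify a summary. That presumes a set without transfers. Table 6 gives one close to the whole safety analysis set.

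**4. Effect on percentages.** Let r be the transfer share and p the true percentage with an AE among subjects actually followed. Then:

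shown percentage = p × (1 − r)

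Both inputs are assumptions. With p = 20%:

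| r | Shown percentage |
|---|---|
| 25% | 20 × 0.75 = 15% |
| 50% | 20 × 0.50 = 10% |
| 70% | 20 × 0.30 = 6% |
| 80% | 20 × 0.20 = 4% |
| 90% | 20 × 0.10 = 2% |

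Attendance at the follow-up visit is scaled by the same factor.

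**5. Effect on event rates.** Take 250 subjects, r = 50%, p = 20%, one event per affected subject, 14 weeks of follow-up and 52.18 weeks per year.
- Followed: 125. Events: 25. Person-years: 125 × 14/52.18 = 33.54.
- Rate: 25/33.54 = 74.54 per 100 person-years.
- The 125 transfers add 125 × 8 s = 1,000 s, about 0.00003 person-years. The rate stays at 74.54.

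**The case against.** The strongest reply is that membership is inferred. SAP 6.8.2 ties the sets to period start and end but does not say that any non-zero interval admits a subject, and the Table 6 boundaries also serve to allocate AEs to periods. The intent to leave transfers out is visible in the amendment rationale. Protocol 14.2 sends decisions on set membership to an analysis set definition document, to be completed before unblinding, which could settle the matter. This stands in part: that document is not available here, so what the final tables would contain is unknown. But Table 6 is the only operational rule in the two documents, it yields a valid period for these subjects, and nothing written takes them out. Evidence of a different intent shows the conflict without resolving it.

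Several stronger readings are tempting and not supported:
- A reader might infer from Protocol 14.2 that the set is empty, since dosing stops at Week 24. That is only a literal reading. The evident meaning is exposed subjects who are in follow-up. The wording fails to settle membership, which is a smaller fault.
- A reader might infer that all off-treatment safety, PK and ADA results are distorted. SAP 6.7.6 summarises PK and ADA for the treatment period, with an extra ADA summary over the whole trial. Follow-up vital signs, laboratory values and ECGs are only listed.
- A reader might infer that unequal transfer will create a difference between arms. The arithmetic allows it, but the documents give no transfer share overall or by arm.

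On attendance, the eCRF option of other with a required specification may let transfers be identified, but they have no category of their own.

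**Conclusion.** The point holds within limits. As written, SAP 6.8.2 and Table 6 place ECZTEND transfers in the safety follow-up analysis set with as little as 8 seconds of follow-up, contrary to the protocol's expectation of a small set, and Protocol 14.2 does not resolve the conflict. The effect is confined to follow-up AE percentages, any tests on them, and the follow-up attendance table. The factor (1 − r) follows from the rules; the illustrative size (20% shown as 10% to 4%) rests on an assumed 20% incidence and an assumed 50% to 80% transfer. Efficacy, treatment-period safety and event rates per person-time are practically unaffected. The text should be corrected before unblinding, unless the analysis set definition document already excludes these subjects.

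**What to change.** - In SAP 5 and 6.8.2, define the safety follow-up analysis set as dosed subjects who did not enter ECZTEND at their Week 26 visit and who have at least one contact dated after the exposure-end date.
- Use that set as the denominator for the follow-up AE tables and for follow-up attendance.
- Show entry into ECZTEND as its own disposition row, by arm.
- Align the wording of Protocol 14.2 with this definition.

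The cost is a few lines of text and one table row, with no new data collection. The drawback is a smaller set selected after randomisation, so comparisons between arms in the follow-up period should be labelled descriptive.
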